8.5.4.6 Faces Pain Scale – Revised (FPS-R)

For subjects aged ≥ 5 years at screening visit, summaries statistics of FPS-R will be reported by study visit for both observed measures and their respective change from baseline based on the Full Analysis Subset (Baseline age ≥ 5 years). Change from baseline of FPS-R over time will be assessed to compare KRN23 therapy with the active control (oral phosphate/active vitamin D) using the GEE approach as outlined in Section 8.5.1 with baseline measures and baseline RSS total score stratification factor included as independent variables.

Descriptive statistics for FPS-R scores as well as its change from baseline will be provided in both continuous and categorical summary. A listing of FPS-R will be provided. Graphs showing change in FPS-R will be provided by treatment group.

8.5.4.7 PD Analysis

The PD parameters will include serum phosphorus, TmP/GFR, serum 1,25(OH)₂D, TRP, and ALP. All PD analyses will be performed on the PD Analysis Set, unless stated otherwise.

Descriptive statistics of PD parameters and their respective change from baseline and percentage change from baseline will be tabulated by treatment group at each study visit.

The change in serum phosphorus from baseline to mean post-baseline values (average of Week 1, 4, 8, 16, 24, 32 and 40 serum phosphorus for Week 40 analysis and Week 1, 4, 8, 16, 24, 32, 40, 52 and 64 serum phosphorus for Week 64 analysis) will be analyzed using an ANCOVA model. Treatment group, baseline age and RSS total score stratification factors will be included as independent variables, baseline serum phosphorus will be included as a continuous covariate. The estimated difference between KRN23 treatment and active control group will be provided along with 95% CI and p-value. The estimated change from baseline within individual treatment groups will also be provided.

PD endpoints at all scheduled visits will be assessed using the GEE approach as outlined in Section 8.5.1 with change from baseline value as dependent variable, baseline measures and baseline age and RSS total score stratification factors included as independent variables.

The proportion of subjects achieving the normal range (3.2-6.1 mg/dL) will be reported by treatment group at each study visit. Similarly, proportion of subjects achieving TmP/GFR within the normal range (2.6 – 4.4 mg/dL) will be reported by treatment group at each study visit.

A listing containing PD parameters such as serum phosphate level, serum 1,25(OH)₂D, TmP/GFR, TRP, and ALP will be provided for each subject.

Graphs showing the change over time in PD parameters for both observed measure and the respective change from baseline will be provided by treatment group.

8.6 Analysis of Other Efficacy Endpoint(s)

8.6.1 Health-related Quality of Life (SF-10 for Children Health Survey)

Descriptive summary statistics of the PHS-10 and PSS-10 scores will be reported by study visit for both observed measures and their respective change from baseline based on the Full Analysis Subset (Baseline Age ≥ 5 years). A listing of PHS-10 and PSS-10 scores will be provided.

8.6.2 Dental Assessment

The number of dental events (dental abscess, dental cavities, tooth extraction, root canal and gingivitis) will be summarized by treatment group at each study visit. A listing of dental events will be provided for each subject.

8.7 Pharmacokinetics

The descriptive statistics for serum KRN23 will be tabulated and the listing of serum KRN23 will be provided based on the PK analysis set.

8.8 Safety Analysis

Safety Analysis Set will be used for the safety analysis. Subjects will be analyzed based on the actual treatment received. Safety variables including AEs, SAEs, events to monitor, safety laboratory assessments, vital signs, renal ultrasound, ECG, ECHO, and anti-KRN23 antibody will be summarized descriptively by treatment group.

8.8.1 Adverse Events

Adverse events will be coded by system organ class and preferred term using the Medical Dictionary for Regulatory Activities.

An AE (classified by preferred term) will be considered a treatment emergent adverse event (TEAE) if it occurred on or after the first dose of investigational product and was not present prior to the first dose, or it was present before the first dose but increased in severity during the study.

Subject incidence of TEAEs will be tabulated as the following:

- Summary of TEAEs by treatment group
- TEAEs by SOC and PT (preferred term) by treatment group (sorted by descending frequency by SOC and PT)

- Related TEAEs by SOC and PT by treatment group (sorted by descending frequency by SOC and PT) or TEAE by greatest relationship, SOC and PT by treatment group
- Serious TEAEs by SOC and PT by treatment group (sorted by descending frequency by SOC and PT).
- Serious and Related TEAEs by SOC and PT by treatment group (sorted by descending frequency by SOC and PT).
- Grade 3 or 4 TEAEs by SOC and PT by treatment group (sorted by descending frequency by SOC and PT). or TEAE by greatest severity, treatment group, SOC and PT
- Deaths by SOC and PT by treatment group (sorted by descending frequency by SOC and PT).
- TEAEs leading to discontinuation of study by SOC and PT by treatment group (sorted by descending frequency by SOC and PT).
- TEAEs leading to discontinuation of treatment by SOC and PT by treatment group (sorted by descending frequency by SOC and PT).
- TEAEs by PT by treatment group (sorted by descending frequency of PT)
- Serious TEAEs by PT by treatment group (sorted by descending frequency of PT)
- Related TEAEs by PT by treatment group (sorted by descending frequency of PT)

Subject incidence for each type of events to monitor will be tabulated as the following:

- By PT by treatment group
- By PT and greatest reported severity by treatment group
- By PT and relationship to study drug by treatment group

Detailed listings for all AEs, serious TEAEs, AEs leading to the discontinuation of study, AEs leading to the discontinuation of treatment, and death will also be generated.

The severity will be based on Common Terminology Criteria for Adverse Events (CTCAE), Version 4.0. If an AE cannot be graded based on CTCAE, the investigator will assign a severity based on 1 = mild, 2 = moderate, 3 = severe, 4 = life threatening, and 5 = Death.

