7.3.1 Inclusion Criteria

Note: All laboratory evaluations required for study eligibility will be determined centrally

Individuals eligible to participate in this study must meet all of the following criteria:

- 1) Male or female, aged 1 to ≤ 12 years with radiographic evidence of rickets with a minimum rickets severity score (RSS) total score of 2.0 as determined by central read
- 2) *PHEX* mutation or variant of uncertain significance in either the patient or in a directly related family member with appropriate X-linked inheritance
- 3) Biochemical findings associated with XLH: Serum phosphorus < 3.0 mg/dL (< 0.97 mmol/L)*
- 4) Serum creatinine below the age-adjusted upper limit of normal *
- 5) Serum 25(OH)D above the lower limit of normal (≥ 16 ng/mL) at the Screening Visit**

- 6) Have received both oral phosphate and active vitamin D therapy for ≥ 12 consecutive months (for children ≥ 3 years of age) or ≥ 6 consecutive months (for children <3 years of age) 7 days prior to the Randomization Visit
- 7) Willing to provide access to prior medical records for the collection of historical growth and radiographic data and disease history.
- 8) Provide written or verbal assent (as appropriate for the subject and region) and written informed consent by a legally authorized representative after the nature of the study has been explained, and prior to any research-related procedures.
- 9) Must, in the opinion of the investigator, be willing and able to complete all aspects of the study, adhere to the study visit schedule and comply with the assessments.
- 10) Females who have reached menarche must have a negative pregnancy test at Screening and undergo additional pregnancy testing during the study. Female subjects of childbearing potential must be willing to use a highly effective method of contraception for the duration of the study plus 12 weeks after stopping the study drug. Sexually active male subjects with female partners of childbearing potential must consent to use a condom with spermicide or a highly effective method of contraception for the duration of the study plus 12 weeks after stopping the study drug.

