7.6.5 Safety Analyses

Full Analysis Set will be used for the safety analysis. Subjects will be analyzed based on the actual treatment received. Safety variables including AEs, SAEs, safety laboratory assessments, vital signs, renal ultrasound, ECG, ECHO, and anti-KRN23 antibody will be summarized descriptively by treatment group.

All AEs will be coded using the Medical Dictionary for Regulatory Activities (MedDRA). The incidence and frequency of AEs will be summarized by System Organ Class, Preferred Term, relationship to study drug, and severity. All reported AEs with onset during the treatment (ie, treatment-emergent AEs) will be included in the analysis. For each AE, the percentage of subjects who experienced at least 1 occurrence of the given event will be summarized by treatment group. Special attention will be given to those subjects who died, discontinued treatment due to an AE, or experienced a SAE.

Clinical laboratory data will be summarized by the type of laboratory test. Reference ranges and markedly abnormal results (specified in the SAP) will be used in the summary of laboratory data. The frequency and percentage of subjects who experience abnormal clinical laboratory results (ie, outside of reference ranges) and/or clinically significant abnormalities (as determined by the Investigator) will be presented for each clinical laboratory measurement. The SAP will provide additional details on the planned safety analyses.

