8.5.4 Adverse Event Reporting

8.5.4.1 General

All AEs (ie, any new or worsening in severity or frequency of a preexisting condition) with onset after the subject signs consent for study participation must be promptly documented on the CRF. The Investigator is responsible for evaluating all AEs, obtaining supporting

documents, and ensuring documentation of the event is adequate. Details of the AE must include severity, relationship to study drug, duration, and outcome.

For subjects not continuing KRN23 treatment under commercial use or another mechanism upon completion of study drug treatment or early withdrawal from this study, a Safety Visit will be conducted 12 weeks \pm 1 week after the last dose of study drug in this protocol. All AEs will be recorded from the time the informed consent is signed through 12 weeks following the last dose of study drug, unless the subject enrolls in another clinical study of KRN23, is treated with commercially available KRN23, or is treated with KRN23 through another mechanism, at which point the collection of AEs within this study is no longer applicable. In addition, the Investigator should report any AE that occurs after this time period that is believed to have a reasonable possibility of being associated with study drug. AEs will continue to be reported either under another KRN23 protocol or per post-approval requirements for safety monitoring, as applicable.

AEs ongoing at 12 weeks following the last dose of study drug should have a comment in the source document by the Investigator that the event has recovered, recovered with sequelae, or stabilized.

8.5.4.2 Serious Adverse Events, Serious Adverse Drug Reactions, and Requirements for Immediate Reporting

Ultragenyx or its designee must be notified of the occurrence of any SAE that occurs during the reporting period within 24 hours of the Investigator, designee, or site personnel's knowledge of the event. SAEs will be reported by completing and submitting SAE report forms to Ultragenyx or designee.

Follow-up SAE information must be submitted in a timely manner as additional information becomes available. All SAEs regardless of relationship to study drug must be followed to resolution or stabilization if improvement is not expected.

All deaths, regardless of causality, occurring from signing of the informed consent until 12 weeks following the last dose of study drug are to be reported as SAEs to Ultragenyx or its designee within 24 hours of knowledge.

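### The SAP's treatment-emergent rule works by preferred term and can drop new same-grade episodes that the protocol's onset rule counts

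*SAP*

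**What the plan says.** SAP 8.8.1 makes the preferred term the unit of classification: "An AE (classified by preferred term) will be considered a treatment emergent adverse event". The condition for the label then runs "TEAE) if it occurred on or after the first dose of investigational product and was not present prior to the first dose". One alternative is allowed, for an event already there: "or it was present before the first dose but increased in severity during the study". No other route is given. A new episode of the same term at the same grade has no way in, and neither does a rise in frequency.

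Protocol 7.6.5 uses onset alone: "All reported AEs with onset during the treatment (ie, treatment-emergent AEs) will be included in the analysis". It then reports, by arm, the percentage of subjects with at least one occurrence of each event. Protocol 8.5.4.1, on what must be reported as an AE, includes "any new or worsening in severity or frequency of a preexisting condition".

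SAP section 1 says that the SAP details the analyses outlined in the protocol, and cites its version of 4 April 2016. The summary of changes for Amendment 1, as far as it is reproduced, lists no change to the treatment-emergent definition.

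**The concern.** The two documents define the same label differently, and the SAP's version is the narrower. Apart from the tables of events to monitor, the AE incidence tables in SAP 8.8.1 are almost all tables of TEAEs, so the definition decides which children appear in them.

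Pre-dose records will exist. AEs are recorded from consent (protocol 7.5.3.13), screening may last up to 8 weeks, and weaning from oral phosphate and active vitamin D starts only after the screening radiographs confirm rickets (protocol 7.5.1). Inclusion criterion 6 requires prior treatment with both control drugs: "Have received both oral phosphate and active vitamin D therapy for ≥ 12 consecutive months", or at least 6 months for children under 3. Only the control arm goes back to these drugs (protocol 7.4.5.1). Protocol Appendix 1 lists nausea, diarrhoea, headache and abdominal pain among their known effects. Such events could plausibly be logged in screening and recur on treatment. The safety objective in protocol section 6 is a comparison with active control, so a rule that removes recurrences could affect the arms unequally.

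**Working it through.** **1. The rules applied to sample records.** The SAP does not define *present*, so both readings are shown.

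| Record | Protocol 7.6.5 | SAP, present = ever recorded | SAP, present = ongoing at first dose |
|---|---|---|---|
| Grade 1 diarrhoea in screening, resolved before first dose; new grade 1 episode on treatment | Counted | Not counted | Counted |
| Grade 1 headache ongoing at first dose, resolves; new grade 1 episode later | New episode counted | Not counted | Not counted |
| Grade 1 nausea before dosing; grade 2 episode on treatment | Counted | Counted | Counted |
| Term first seen after first dose | Counted | Counted | Counted |

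The rules differ on the second row under either reading, and on the first row under one of them. The SAP also does not say whether medical history counts towards *present* or only the AE log from consent.

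**2. How a loss would arise.** The documents give no AE rates and attach no figure to this rule, so there is no plan figure to reproduce. Every rate below is an assumption. Let q be the share of children with the term before first dose (equal in expectation across arms by randomization), r1 and r0 the risk of an on-treatment episode with and without the term beforehand, and s the share of repeat episodes with higher severity.

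- Onset rule: (1 − q)·r0 + q·r1
- SAP rule, ever-recorded reading: (1 − q)·r0 + q·r1·s
- Loss: q·r1·(1 − s)

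Example for control with q = 0.1, r1 = 0.6, r0 = 0.2, s = 0: onset 0.9 × 0.2 + 0.1 × 0.6 = 0.24; SAP 0.9 × 0.2 = 0.18. With 30 per arm (SAP 3.5) that is 7.2 against 5.4 children.

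**3. Range.** Case A assumes that recurrence depends on history (control r1/r0 = 0.6/0.2, KRN23 0.2/0.1). Case B assumes that it does not (0.4/0.4 and 0.1/0.1). The arm columns use s = 0.

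| Case | q | Control: onset → SAP | KRN23: onset → SAP | Control − KRN23 by onset, points | By SAP, s = 0 | By SAP, s = 0.2 |
|---|---|---|---|---|---|---|
| A | 0.1 | 24% → 18% | 11% → 9% | 13 | 9 | 10 |
| A | 0.3 | 32% → 14% | 13% → 7% | 19 | 7 | 9 |
| A | 0.5 | 40% → 10% | 15% → 5% | 25 | 5 | 9 |
| B | 0.1 | 40% → 36% | 10% → 9% | 30 | 27 | 28 |
| B | 0.3 | 40% → 28% | 10% → 7% | 30 | 21 | 23 |
| B | 0.5 | 40% → 20% | 10% → 5% | 30 | 15 | 18 |

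If the risks are the same in both arms, both lose the same share and a difference of 0 stays 0. A term that cannot occur before KRN23 (q = 0), such as an injection site reaction to it, loses nothing.

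**The case against.** Protocol 7.6.5 leaves further detail to the SAP, and protocol 8.5.4.1 is a reporting definition, not a definition of treatment-emergent. Both points are right. But 7.6.5 does say what treatment-emergent means, and the SAP narrows it without saying so.

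If *present* means ongoing at first dose, a resolved screening event no longer blocks a later one. That stands and shrinks the loss, but does not remove it, as the headache record shows.

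A reader might infer that dental abscesses or worsening nephrocalcinosis vanish from the safety report. The documents do not support that. SAP 8.6.2 counts dental events by arm and visit. SAP 8.8.7 gives nephrocalcinosis grades by arm and a shift table. Nephrocalcinosis is among the events to monitor in Appendix 10, whose tables are not expressly limited to TEAEs. All AEs are listed. Ordinary terms such as nausea or headache have only the listing, which is not an incidence comparison.

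A reader might also infer from the 6 to 12 months of prior therapy that control-drug effects are shown to be filtered out. They are not. If the look-back is the AE log, it covers at most the screening window, part of it off therapy, and a stable tolerated effect may never be logged as an AE.

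**Conclusion.** The definitions conflict, and the SAP's literal rule omits new same-grade on-treatment episodes from the overall, SOC/PT and related TEAE tables. This rests on the text alone. The other TEAE tables use the same label, but lose an event only where the pre-dose event had the same or a higher grade.

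The size is unknown. It depends on event rates, the meaning of *present* and the look-back source, none of which the documents give. The tables above show direction and sensitivity; they are not estimates. A larger loss for control-drug effects in the control arm is a reasonable inference, because only controls resume those drugs. It would understate control-arm toxicity and so would not favour KRN23 on those terms. A claim that the safety comparison is shown to be distorted, or distorted by a given number of points, goes beyond the documents. Safety summaries are descriptive and no efficacy conclusion is affected, but the correction is cheap and should be made.

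**What to change.** In SAP 8.8.1, delete the preferred-term qualifier from the definition and state: *an AE record is treatment-emergent if its start date is on or after the first dose of assigned treatment, or if it started before the first dose and increased in severity on or after it.* Keep preferred term for tabulation only. *Assigned treatment* avoids a wording gap, since protocol section 4 reserves *investigational product* for KRN23.

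Instruct sites to record a worsening in frequency of a pre-existing condition as a new AE with its own onset date. This is consistent with protocol 8.5.4.1 and lets the onset rule capture it. Frequency should not be a derived criterion: the AE details that 8.5.4.1 requires are severity, relationship, duration and outcome.

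The cost is a short SAP edit, a change to the derivation code and the recording instruction. The date and severity parts use what the SAP already relies on, including the imputation of partial start dates in SAP 7.2.1. The downside is that TEAE percentages become somewhat higher in both arms.

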8.8.2 Clinical Laboratory Parameters

Descriptive statistics for clinical laboratory values and changes from the baseline values at each assessment time point will be presented by treatment group for laboratory parameters listed in [Appendix 2](#). Shift table for iPTH at each scheduled visit will be provided to assess to the normality over time. Listings for all clinical laboratory parameters and all abnormal laboratory parameters will be provided for each subject.

8.8.3 Vital Signs

Descriptive statistics for vital signs (systolic and diastolic blood pressures, systolic and diastolic blood pressure percentiles, pulse rate, and weight) and changes from baseline values at each visit and at the end of study will be presented by treatment group.

The blood pressure will be summarized by study visit in mmHg and percentile to assess the blood pressure change over time.

Heart rate and heart rate percentile category will be tabulated over time by treatment group.

8.8.4 Concomitant Medications

Each medication will be coded to a preferred name and an Anatomic Therapeutic Classification (ATC) code using WHODrug. The number and percentage of subjects taking each concomitant medication will be displayed by medication class (anatomical classification) and preferred name for each treatment group. This display will be created for the safety analysis set. A concomitant medication listing will also be made. Prior medications, e.g. medications that were stopped before the first dose of study therapy, will also be listed.

8.8.5 Physical Examination

Physical exam results will include the assessment of general appearance; head, eyes, ears, nose, and throat (HEENT); the cardiovascular, dermatology, lymphatic, respiratory, gastrointestinal, genitourinary, musculoskeletal, neurological systems. The number and percentage of subjects with Normal/Abnormal assessment for each body system will be summarized by visit and treatment group. All physical examination assessments will be listed.

8.8.6 Pregnancy Test

Subject level listing for pregnancy test results will be created for those who had positive pregnancy test.

8.8.7 Renal Ultrasound

Renal ultrasound will be conducted with findings of nephrocalcinosis graded on a 5-point scale by a central reader. These results will be summarized by time point and presented by treatment group. Furthermore, a grade shift table summarizing changes from baseline by time point will also be created.

A listing of renal ultrasound/nephrocalcinosis scores will also be provided.

8.8.8 ECG

Descriptive statistics for ECG parameters (heart rate, RR interval, PR interval, QRS duration, QT interval, and QTc) and changes from baseline values at each assessment time point to the end of study will be presented by treatment group. The QTc will be calculated using both the Bazett and Fridericia corrections.

ECG parameters will be summarized by study visit, by the maximum post-baseline value, change from baseline and maximum change from baseline. Shift from baseline to post-baseline visits in overall ECG assessment (normal or abnormal) will also be provided.

A listing of all ECG parameters including the overall assessment will also be created.

